18.4 Analyses Datasets (statistical populations)

18.4.1 Intention to treat (ITT) population

The ITT population will include all randomized subjects with at least one performance measurement after implantation. The final definition will be made at the clean-file meeting for Part I before the breaking the code.

18.4.2 Per protocol (PP) population

The Per Protocol population will include all subjects in the ITT-population without significant protocol violations. Subjects identified as protocol violators will be documented and agreed on at the clean-file meeting for Part I before the database lock for Part I.

18.4.3 Safety population

Safety population will include all subjects who have received at least one implant.

18.5 Performance Analyses

18.5.1 Primary efficacy analysis

Primary efficacy analysis will be the comparison of change in ISQ highest value for coated implant with change in ISQ highest value for the uncoated implant on the “index implant” from day 1 to 12 weeks visit with Fisher’s non-parametric permutation test on the ITT-population at significance level 0.05. For primary efficacy variable the 95% confidence interval for the mean difference between the coated and the uncoated implants is obtained by inversion of Fisher’s non-parametric permutation test by means of simulation.

If the 12 months ISQ highest values are missing Last observation carry forward (LOCF) will be used from 8 weeks.

If significant differences are found between the two randomised groups in important baseline predictors a complementary primary efficacy analyses will be performed adjusted for these variables using analysis of covariance (ANCOVA).

Sensitivity analyses will be performed for primary efficacy variable change in ISQ highest value from day 1 to week 12 between coated and uncoated implants with multiple imputations for missing values using analysis of variance for the unadjusted analysis and analyses of covariance for the adjusted analysis if needed. When using multiple imputations LOCF should not be applied.

Complementary analyses between the two randomized groups of the primary efficacy variable will be done on the PP-population.

Primary efficacy analysis will be presented per centre and a separate analysis will also be performed in order to study centre effect for primary variables. In case of few centres, centre will be analysed as fixed effect.

18.5.2 Secondary efficacy analyses Part I

Secondary performance analyses for Part I will be the comparison will be the comparison between the two randomized groups regarding all the secondary performance variables given in section 11.1.2 using the statistical methodology given in sections 18.2 above on the ITT-population. Complementary analyses between the two randomized groups of secondary performance variables will be done on the PP-population.

18.5.3 Secondary efficacy analyses Part II

Secondary performance analyses for part II will be the comparison will be the comparison between the two randomized groups regarding all the secondary performance variables given in section 11.1.3 using the statistical methodology given in sections 18.2 above on the ITT-population. Complementary analyses between the two randomized groups of secondary performance variables will be done on the PP-population.

18.5.4 Exploratory performance analyses

Univariable and multivariable analyses of baseline predictors to primary and selected secondary outcome variables will be performed using linear and/or logistic univariable regression analyses followed by forward stepwise multivariable linear and/or logistic regression analyses.

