18.2 General methodology

The design of the study is a two parallel group design. The main efficacy analyses will be performed on the Intention-to-Treat (ITT) populations between the two groups. Complementary performance analyses will be performed on the Per Protocol (PP) population. See section 18.4 below.

For comparison between the two randomized groups regarding “index implant”, Fisher’s non-parametric permutation test will be used for continuous variables, Mantel-Haenszel chi-square test for ordered categorical variables, and Chi-square test for non-ordered categorical variables and Fisher’s exact test for dichotomous variables.

For primary efficacy variables and for other important continuous efficacy variables the 95% confidence interval for the mean difference between the two groups will be obtained by inversion of Fisher’s non-parametric permutation test by means of simulation.

For comparison between the two randomized groups regarding analysis of all teeth within subjects a mixed model with random effects analysis adjusting for within subject correlation will be used.

If significant clinical relevant differences are found between the two randomised groups in important baseline variables, then complementary efficacy analyses will be performed adjusted for these variables.

For comparison over time within randomized groups Fisher’s non-parametric permutation test for paired observations will be used for change in continuous and Sign test for change in ordered categorical variables or change in dichotomous variables.

The distribution of the variables will be given as mean, SD, median, minimum and maximum for continuous variables and as number and percentages for categorical variables.

Time to loss of implant will be described with Kaplan-Meier curves and analysed with Log-rank test between the two randomised groups.

All significance tests will be two-sided and conducted at the 5% significance level.

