18.8 Determination of sample size

The power analysis based on Abtahi et al. 2012: The SD for change in ISQ value from placement to month 6 was 5.3 in the active group and 5.4 in the control group. In order to be able to find a clinical difference of five ISQ highest values in change between placement and 12 weeks between the coated and the uncoated group with Fisher's non-parametric permutation test with 90% power 28 evaluable subjects are needed in each group assuming a SD for change in ISQ in each group of 5.6 and a significance level 0.05. Thirty-one subjects will be randomized to each study group to compensate for 10% drop-out. A total of 62 subjects will be randomized to the two groups.

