For comparison over time of index implants within randomized groups Fisher's non-parametric permutation test for paired observations will be used for change in continuous and Sign test for change in ordered categorical variables or change in dichotomous variables. When all implants are analyzed the same methods as specified above, i.e. mixed and GEE models will be applied.

The distribution of the variables will be given as mean, SD, median, minimum and maximum for continuous variables and as number and percentages for categorical variables.

The survival rate of implant (implant loss) will be described with Kaplan-Meier curves with 95% CIs adjusted for within-subject correlation and analyzed with suitable Log-rank test, also adjusted for within-subject correlation, between the two randomised groups.

All tests will be two-tailed and conducted at 0.05 significance level. All analyses will be performed by using SAS® v9.2 (Cary, NC).

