#### 4.8.4 Exploratory Efficacy Analyses

Univariable and multivariable analyses of baseline predictors to primary efficacy variable will be performed using mixed models as specified in *General Methodology* above followed by forward stepwise multivariable model on the ITT population on all implants. The variables to be examined are:

- Age
- Sex
- Bone quality
- Bone quantity
- Implant position
- Smoking
- Alcohol
- Diabetes.

STATISTISKA KONSULTGRUPPEN		Statistical Analysis Plan	
Protocol: A randomized, double blind, parallel study to evaluate the performance and safety of the Zolidd One ExHex dental implant in subjects with partial edentulism		Protocol No: ADD-001	Version: 1.0 Page 14 of 18

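### The exploratory predictor model uses forward stepwise selection with no entry rule although the SAP lists only eight candidates; weak effects that pass are overstated, and one full model reported in full avoids this

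*Protocol*

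**What the plan says.** The Protocol places the analysis under "18.5.4 Exploratory performance analyses". Baseline predictors of the primary and selected secondary outcomes are examined one at a time, "followed by forward stepwise multivariable linear and/or logistic regression analyses". No candidates are named there.

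SAP 4.8.4 narrows this to the primary efficacy variable and to mixed models, "followed by forward stepwise multivariable model on the ITT population on all implants". It introduces its list with "The variables to be examined are" and gives eight: age, sex, bone quality, bone quantity, implant position, smoking, alcohol and diabetes.

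Neither section states an entry or stopping threshold, shrinkage, internal validation or any allowance for selection. Neither says how the selected predictors will be reported. The only error-rate rule is the general one: "All significance tests will be two-sided and conducted at the 5% significance level" (Protocol 18.2) and "All tests will be two-tailed and conducted at 0.05 significance level" (SAP 4.1).

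SAP 7.1 gives the results two tables, 14.2.2.1 (maximum ISQ at 12 weeks) and 14.2.2.2 (marginal bone height at 24 months).

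**The concern.** Forward selection keeps a variable only if its estimate is large relative to its standard error. When the true effect is weak, the samples in which it passes are those in which chance has enlarged it, so the estimate shown is too big on average. A variable that does not pass has no adjusted estimate, and a reader may take its absence as evidence of no effect.

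Bone quality is where this matters most. Protocol 9.1 and 9.7 rest the expected benefit of the coating on sites with poor bone, so the size of a bone-quality effect on stability is likely to be quoted. Selection is also unnecessary here, because the SAP has already fixed a short list.

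**Working it through.** **Inputs.** From the documents: 62 subjects (Protocol 18.8: "A total of 62 subjects will be randomized to the two groups"), SD of change in ISQ 5.6, eight candidates (SAP 4.8.4), two-sided 0.05. Assumed: entry at p<0.05, taken from the general testing rule because no entry rule is given; one implant per subject; distributions of the candidates.

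**1. The plan's own figure.** Protocol 18.8 states "90% power 28 evaluable subjects are needed in each group assuming a SD for change in ISQ in each group of 5.6" for a difference of 5. The normal approximation gives 2 × (1.960 + 1.282)² × 5.6² / 5² = 26.4, so 27 per group. With the noncentral t, power is 89.6% at 27 and 90.7% at 28, so 28 is reproduced. Then 28 × 1.10 = 30.8, so 31 per group and 62 in all. The documents give no figure for the stepwise analysis.

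**2. Why selection overstates a weak effect.** Passing at p<0.05 means that the estimate exceeds its own CI half-width. Under one set of assumed distributions, the half-width for bone quality in the selected model is about 1.95 ISQ per class. If the true effect is 1.0, it can then be reported only as roughly 1.95 or more.

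The same holds on a standardised scale. The standard error of a slope is about 1/√62 = 0.127, and the critical t is about 2.00, so the bar is about 0.254. That is 1.7 times a true slope of 0.15, but only half of a true slope of 0.50.

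**3. Simulated size of the bias** (one true predictor, seven null, n = 62, entry 0.05, 4000 runs each):

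| True standardised slope | Selected | Mean estimate / truth when selected | 95% CI coverage when selected |
|---|---|---|---|
| 0.15 | 22% | 2.1 | 86% |
| 0.25 | 47% | 1.4 | 93% |
| 0.35 | 74% | 1.16 | 97% |
| 0.50 | 95% | 1.03 | 95% |

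In ISQ units with SD 5.6, a true bone-quality effect of 1 per class averaged 2.1 to 2.5 when selected, depending on the assumed distributions. A true effect of 2 averaged about 2.5 to 2.9.

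**4. The full eight-variable model.** With every coefficient reported, a true 1.0 per class averages 0.98, and coverage is about 95%. The half-width for bone quality rises to about 2.3 ISQ per class.

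**5. False predictors.** For eight independent tests at 0.05, 1 − 0.95⁸ = 33.7%. With no true predictor, simulated forward selection names at least one variable in 31% to 35% of runs with near-independent candidates, and in 24% when their correlation is 0.5. The full model shows at least one p<0.05 in 31% to 32%. If the unstated entry level were 0.10 or 0.15, stepwise would name at least one in 45% to 59% or 58% to 74%.

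**6. Clustering.** With 1 to 6 implants per subject (assumed distribution), a within-subject correlation of 0.2 or 0.5 treated as known, and entry at 0.05, at least one null variable was selected in 30% or 32% of runs. The size of the bias in step 3 was not simulated for the clustered model.

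**The case against.** The strongest reply is that the usual charges against stepwise selection do not separate it from the alternative. A reader might infer that stepwise selection causes a false predictor in about a third of trials. It does not: at entry 0.05, step 5 gives practically the same rate for the full model, because the figure comes from testing eight variables. Nor does 62 drive it; with 56 subjects the rate is 34%.

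A reader might also infer that the stepwise CIs are simply wrong, since under the null none of those shown covers zero. That is close to a tautology, because entry at p<0.05 already means that the CI excludes zero. Significant coefficients picked out of the full model behave the same way: a true 1.0 per class averaged 2.20 among significant full-model estimates, against 2.09 among selected stepwise ones in the same simulation. For a truly predictive variable, coverage after selection stays at about 85% to 97%.

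Both points stand. They mean that the gain comes from reporting all coefficients, and that it is lost if the reader looks only at the significant ones.

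It is also fair that the analysis is labelled exploratory, that no claim or decision in the documents depends on it, and that univariable results are planned for all eight variables, so an omitted variable still has an unadjusted estimate. This limits the importance of the point but does not make the selected estimates unbiased.

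**Conclusion.** The point holds as a low-priority improvement. Both documents prescribe selection from a list short enough to need none, and the entry rule is missing. Where only selected variables are shown, a weak effect is overstated about twofold (1 ISQ per bone-quality class), a moderate one by about 1.4 times (slope 0.25), and a strong one by about 3% (slope 0.50).

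These sizes assume entry at 0.05, SD 5.6, 62 subjects with one implant each, and invented predictor distributions. The SAP's model uses all implants, which may give more information on implant-level variables and so less bias for them.

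A reader might further infer that the plan commits to presenting the selected model with ordinary p-values and CIs, as if its variables had been fixed beforehand. The documents do not say so; they are silent on reporting, and the bias arises only if they report selected estimates alone. The primary permutation test, the sample size and the secondary comparisons are unaffected.

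**What to change.** In Protocol 18.5.4 and SAP 4.8.4, replace the stepwise step with one pre-specified mixed model on all implants containing all eight listed variables. Fix the coding of the multi-level ones beforehand. Report every coefficient with its 95% CI whether or not it is significant, keep the univariable results as description, and label the tables hypothesis-generating. Say explicitly that predictors are not to be singled out by p<0.05, since the roughly 30% chance of at least one null variable reaching it remains.

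In the same edit, name the outcomes: SAP 4.8.4 refers to the primary efficacy variable (change in ISQ), whereas the SAP 7.1 table titles refer to ISQ at 12 weeks and bone height at 24 months. If stepwise selection is kept after all, state the entry and stopping rule and add shrinkage or a bootstrap check.

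The cost is a wording change and one simpler model. The adjusted CIs widen somewhat, for bone quality from about 1.95 to about 2.3 ISQ per class in half-width under the assumed distributions, or about 18% (2.3/1.95 = 1.18).

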18.6 Safety analysis

Adverse events (AE) will be listed and summarised by body system, incidence, severity, seriousness and duration/outcome. All AE's will be coded with MedDRA dictionary and tabulated by Preferred Term (PT) code and System Organ Class (SOC) code. Serious Adverse Events (SAEs) or Serious Adverse Device Effects (SADEs) will be summarised separately. Any premature discontinuations due to adverse events and deaths will be listed and summarised by treatment group.

Time to loss of implant will be described with Kaplan-Meier curves and analysed with Log-rank test between the two randomised groups.

All safety analyses will be performed on the safety population.

18.7 Analysis of baseline variables

All baseline variables will be tabulated by randomised group and analysed by randomised group according to the statistical methods given in the statistical methods given in section 18.2 above on both the ITT population and PP population.

18.8 Determination of sample size

The power analysis based on Abtahi et al. 2012: The SD for change in ISQ value from placement to month 6 was 5.3 in the active group and 5.4 in the control group. In order to be able to find a clinical difference of five ISQ highest values in change between placement and 12 weeks between the coated and the uncoated group with Fisher's non-parametric permutation test with 90% power 28 evaluable subjects are needed in each group assuming a SD for change in ISQ in each group of 5.6 and a significance level 0.05. Thirty-one subjects will be randomized to each study group to compensate for 10% drop-out. A total of 62 subjects will be randomized to the two groups.

18.9 Randomisation procedure

Subjects will be randomised in proportions 1:1 to receive either coated or uncoated screw implants. This will be in a balanced block design; the sequences and sizes of blocks may also be randomised. The aim being to maintain a balance in subject numbers across all centres in the investigation at any one time, provided recruitment rates are similar.

Once generated the central randomisation schedule will be kept blinded for the study monitor, investigators and data management staff. After un-blinding for analyses of Part I the study monitor and investigator should still be blinded regarding study patients.

Coated implants batches will be kept separate from uncoated batches and suitably labelled to allow easy identification prior to final packaging before sterilisation. Placement in final packaging and labelling with standard labels including Subject ID Number will be supervised and double checked. Further details of this process are included in the Investigator brochure as is the procedure for emergency code breaking.

18.10 Expected drop-out rates

It is anticipated that the dropout rate for this investigation should be low and based on previous work a dropout rate of less than 5% would be expected. The above figures include sufficient subjects to cover this margin.

18.11 Interim analysis

No interim analysis is planned.

18.12 Reporting deviations from original statistics plan

Deviation from original statistical plan will be specified in the statistical Analysis Plan (SAP).

18.13 Sub-group analysis plans

Interaction analyses will be performed between baseline variables and group effect, coated vs uncoated, regarding primary efficacy variable.

Interactions effect with ($p<0.10$) will be followed by suitable subgroups analyses for that baseline variable.

18.14 Handling missing or spurious data

Last observation carry forward (LOCF) will be used from 8 weeks to 12 weeks in Part I and from 12 months to 24 months in Part II. For primary efficacy analyses a sensitivity analysis will be performed with multiple imputations.

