### 3.2.3 *Secondary Efficacy Variables for Part II*

- Post-surgical complications and other adverse events up to month 24 post-implantation visit for all implants
- Survival rate up to 24 months for all implants
- Marginal bone height at day 1, week 8, week 12, month 12 and month 24 for all implants

STATISTISKA KONSULTGRUPPEN		Statistical Analysis Plan	
Protocol: A randomized, double blind, parallel study to evaluate the performance and safety of the Zolidd One ExHex dental implant in subjects with partial edentulism		Protocol No: ADD-001	Version: 1.0 Page 10 of 18

- Change in marginal bone height from day 1 to week 8, week 12, month 12 and month 24 for all implants
- Occurrence of signs associated with peri-implantitis at month 12 and month 24 for all implants

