#### 4.8 Efficacy Analyses

##### 4.8.1 Primary Efficacy Analysis

Primary efficacy analysis will be the comparison of change in ISQ highest value for coated implant with change in ISQ highest value for the uncoated implant on the “index implant” from day 1 to 12 weeks visit with Fisher’s non-parametric permutation test on the ITT-population at significance level 0.05. For primary efficacy variable the 95% confidence interval for the mean difference between the coated and the uncoated implants is obtained by inversion of Fisher’s non-parametric permutation test by means of simulation.

If the 12 weeks ISQ highest values are missing Last observation carry forward (LOCF) will be used from 8 weeks, if available. For the cases of implant loss ISQ = 0 at 12 weeks will be imputed in the main analysis, i.e. resulting in negative difference in ISQ for the subject. For the cases where week 8 and week 12 values are not available due to other reasons than implant loss, same value as baseline value will be imputed, i.e. the difference of 0 will be imputed.

Primary efficacy analysis will be presented per centre and a separate analysis will also be performed in order to study centre effect for primary variable. In case of few centres, centre will be analyzed as fixed effect.

If significant differences are found between the two randomised groups in important baseline predictors a complementary primary efficacy analyses will be performed adjusted for these variables using analysis of covariance (ANCOVA).

Following sensitivity analyses will be performed for the primary efficacy variable:

- Multiple imputations: using analysis of variance for the unadjusted analysis and analyses of covariance for the adjusted analysis if needed. When using multiple imputations LOCF should not be applied. For the sensitivity analysis missing values due to lost implants will be handled with multiple imputation. Following rules will be applied:
  - The multiple imputation will be performed separately for the two study treatment groups to avoid cross-contamination of imputation models between the groups, using PROC MI procedure in SAS version 9.4 and fully conditional specification (FCS) with regression method (REG), per treatment group.
  - The following seed will be used for both groups: 545399
  - The outcome variable of change in ISQ from day 1 will be imputed

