#### 4.8.3 Secondary Efficacy Analyses Part II

Secondary efficacy analyses for Part II will be the comparison between the two randomized groups regarding all the secondary efficacy variables given in section 3.2.3 using the statistical methodology given in sections 4.1 above on the ITT-population.

Complementary analyses between the two randomized groups of secondary efficacy variables will be done on the PP-population.

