#### 4.8.6 Handling of Missing or Spurious Data

The missing data for the primary efficacy variable will be handled as specified in the section 4.8.1 above.

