### 6 CHANGES OF ANALYSIS FROM PROTOCOL

This statistical analysis plan has been written and finalised prior to database lock and revealing of randomized treatment groups. Following changes to protocol were made:

- Added survival rate up to 12 weeks for all implants in Part I analysis/report.
- Marginal bone height will only be analyzed in Part II analysis/report for all study visits.
- ITT population has been changed from 'all randomized subjects with at least one performance measurement after implantation' to 'randomized subjects with at least one study implant' including few specific cases as described in section 2.1.1.
- The imputation of missing data has been updated to also handle implant loss cases.

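### The SAP has not replaced protocol 18.14's month-12-to-24 LOCF in Part II; as written, it fills missing month-24 bone height and peri-implantitis status with month-12 values

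*Protocol*

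**What the plan says.** Protocol 18.14 sets the missing-data rule for both parts: "Last observation carry forward (LOCF) will be used from 8 weeks to 12 weeks in Part I and from 12 months to 24 months" (the latter for Part II). It plans multiple imputation as a sensitivity analysis for the primary efficacy analyses only. Protocol 18.12 makes the SAP the place where departures from the protocol's statistics are recorded.

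The SAP says this:
- Section 4.8.6, the counterpart of protocol 18.14, has one sentence: "The missing data for the primary efficacy variable will be handled as specified in the section 4.8.1 above".
- Section 4.8.1 sets the loss rule for the primary variable: "For the cases of implant loss ISQ = 0 at 12 weeks will be imputed in the main analysis".
- Section 4.8.3 begins "Secondary efficacy analyses for Part II will be the comparison between the two randomized groups" and refers to section 4.1 for methods. Section 4.1 names mixed and GEE models for data with several observations per subject and gives no missing-data rule.
- Section 6 lists four changes from the protocol. The only one on missing data reads: "The imputation of missing data has been updated to also handle implant loss cases".

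Apart from survival and adverse events, the Part II variables assessed at both late visits (SAP 3.2.3) are "Change in marginal bone height from day 1 to week 8, week 12, month 12 and month 24 for all implants", with bone height itself, and "Occurrence of signs associated with peri-implantitis at month 12 and month 24 for all implants".

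**The concern.** For an implant measured at month 12 and not at month 24, carry-forward makes the month-24 change from day 1 equal to the month-12 change and counts it as a measurement. If bone loss continues after month 12, the arm's month-24 loss is understated. For peri-implantitis, new cases are missed and resolved ones are kept. An implant lost after month 12 would keep a bone height although it is no longer in the jaw. The SAP deals with implant loss for week-12 ISQ but gives no equivalent for bone height.

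Month 24 is the last time point for both outcomes, and SAP 1.2 and section 6 move every bone-height analysis into Part II. On the same reading, the planned prediction table for 24-month bone height (SAP 7.1, table 14.2.2.2) would also take in carried values. As things stand, one analyst could follow protocol 18.14 and another SAP 4.1 alone, and they could report different month-24 results from the same data.

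**Working it through.** **Does the rule survive?** Protocol 18.14 sets it and 18.12 says where a change belongs. SAP 4.8.3, 4.8.6 and section 6 are silent on it, and SAP 4.1 does not say that its models replace it. It is therefore neither withdrawn nor implemented. That it covers bone height and peri-implantitis follows from its general wording; neither document says so expressly.

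**The plan's own figure.** The documents give no Part II rate to reproduce. Their one computed design figure, 28 evaluable per group (protocol 18.8: difference 5, SD 5.6, 90% power, two-sided 5%), reproduces: a t-test needs 27.36, rounded up to 28. It concerns week-12 ISQ and enters here only through the 31 randomised per arm.

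**Inputs**
- 31 subjects per arm (protocol 18.8) with 1–6 implants each (protocol 8.1): 31–186 implants per arm.
- m, the share seen at month 12 and missing at month 24: 1, 5 and 10%. The 10% is the whole allowance in protocol 18.8 falling after month 12; 5% is the ceiling in 18.10; 1% is assumed. This is 0.3–3.1 subjects per arm.
- g, mean loss from month 12 to 24: 0.1–0.5 mm (assumed). SD of change: 0.5–1.0 mm (assumed).
- q, the share lost after month 12: 0–2% (assumed). d, lost implants' month-12 loss minus retained implants' month-24 loss: −0.5 to +1.0 mm (assumed).
- Peri-implantitis (all assumed): month-12 prevalence p = 10%, new cases i = 0–10%, resolution r = 0–50%.

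**Bone height, one arm.** If missing implants progress like the others, reported minus true mean loss = −m × g. In size: 0.01 × 0.1 = 0.001; 0.05 × 0.5 = 0.025; 0.10 × 0.5 = 0.05 mm.

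**Bone height, between arms.** Error in (uncoated minus coated loss) = mC × gC − mU × gU.
- Equal m and g: 0.
- Equal m, gU = 0.5, gC = 0.1: size 0.4 × m = 0.004, 0.02 and 0.04 mm at m = 1, 5 and 10%.
- Extremes of these ranges: ±(0.10 × 0.5 − 0.01 × 0.1) = ±0.049 mm.
- Scale: with one implant per subject, SE = SD × √(2/31) = 0.127 mm (SD 0.5) or 0.254 mm (SD 1.0). So 0.049 mm is 0.39 or 0.19 SE.

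**Lost implants carried forward.** Shift in the arm's mean loss = q × d: 0.02 × (−0.5) = −0.01 mm to 0.02 × 1.0 = +0.02 mm.

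**Peri-implantitis.** Reported minus true = m × [p × r − (1 − p) × i]. At m = 10%: 0.10 × (−0.9 × 0.10) = −0.9 percentage points, and 0.10 × (0.10 × 0.5) = +0.5. At m = 1%: −0.09 and +0.05.

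**Other assumptions give more.**
- 20% missing with g = 0.3 mm understates an arm by 0.20 × 0.3 = 0.06 mm.
- 5% against 20% missing, same g = 0.3 mm: a spurious difference of 0.15 × 0.3 = 0.045 mm.
- 20% missing, of whom 20% develop new signs: 0.20 × 0.20 = 4 percentage points.
- One to three of 31 implants lost, each with 1–4 mm of unrecorded further loss: 1 × 1/31 = 0.03 to 3 × 4/31 = 0.39 mm of arm-mean loss hidden.

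**Price of using observed data.** SE relative to complete data = √(ρ² + (1 − ρ²)/(1 − m)), where ρ is the month 12–24 correlation (assumed 0.5–0.9). It runs from 1.001 (m = 1%, ρ = 0.9) to 1.041 (m = 10%, ρ = 0.5), so intervals are about 0.1–4% wider.

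**The case against.** The strongest reply is that the SAP has already moved on. Its missing-data section covers only the primary variable, its Part II section points to mixed and GEE models that need no imputation, and section 6 says the imputation was updated. A statistician following the SAP could reasonably analyse Part II without LOCF. This stands in part: the documents leave the Part II rule unresolved and do not show that LOCF will be used. It does not remove the point. Section 4.1 brings in those models for within-subject dependence, and they can equally be fitted to filled-in data. The update in section 6 concerns implant loss, for which the only rule given is for week-12 ISQ.

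It can also be said that bone height after loss is undefined rather than missing, so 18.14 was never meant for it. Neither document says so. The lost-implant consequence is a reading of general wording, and it arises only for losses after the month-12 measurement.

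On timing, protocol 18.1 plans a blinded Part II review, and SAP 1.2 has bone data locked and analysed once, at study end. Breaking the Part I code therefore reveals no bone-height comparison. That weakens any strict deadline. However, protocol 18.9 names only the monitor and investigator as still blinded afterwards, so settling the rule earlier is safer.

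Finally, the effect is small on most plausible inputs. That is accepted.

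**Conclusion.** The point holds as an unreplaced rule that gives a worse answer than models the SAP already names. It applies to implants with a month-12 value and no month-24 value, and to two secondary outcomes. The size is probably small: up to 0.05 mm per arm, up to 0.049 mm between arms (0.2–0.4 SE), and −0.9 to +0.5 percentage points for peri-implantitis. All of these rest on assumed rates and are illustrations, not bounds; the wider assumptions above exceed several of them.

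A reader might infer more than the documents support:
- That the SAP commits to LOCF in Part II. It is silent.
- That change between months 12 and 24 is zeroed for everyone. Only implants missing at month 24 are touched, and the endpoint is change from day 1.
- That the coated arm is favoured. The between-arm error can have either sign and is zero if the arms are alike.
- That survival or the primary result is compromised. Survival uses Kaplan-Meier and log-rank methods (SAP 4.1), and the week-12 ISQ analysis has its own rules (SAP 4.8.1).

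**What to change.** 1. In SAP 4.8.6 state that LOCF is not used in Part II, and list this in section 6 as a change from protocol 18.14.
2. Analyse bone height with a mixed model of all observed visits (day 1, weeks 8 and 12, months 12 and 24), implants nested in subject, with between-group contrasts of change from day 1 at months 12 and 24. Analyse peri-implantitis by GEE on observed visits, clustered by subject, with contrasts at the same two visits.
3. State that no value is carried forward after implant loss and that loss is reported in the survival analysis. Say openly that the mixed-model month-24 contrast, under missing at random, implicitly extrapolates lost implants as if still in place. Read it beside the survival result and show the observed month-24 summary among implants in place.
4. Do not transfer the multiple imputation of SAP 4.8.1 as it stands: it imputes for lost implants and is written for one value per subject. A sensitivity analysis for these outcomes is optional.
5. Settle this before any unblinded Part II outcome data are analysed, preferably before the Part I code is broken.

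The cost is SAP text, one model specification per outcome and a little more analysis work; no new data are needed. Intervals widen by about 0.1–4% against complete data under the assumptions above. The mixed model assumes missing at random, and standard GEE missing completely at random.
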